12. REGULATORY AND ETHICAL ASPECTS OF THE STUDY

12.1. Authorization for the study

In the case of a non-interventional study, the Protocol and the Patient Information Sheet with an informed consent form for participation in the observational study must be approved by the local ethics committee (LEC) of the institution before the study.

Patients cannot participate in the study until the study is approved by the Council of Ethics and LEC of the institution.

12.2. Ethical Compliance

The investigators and the study team, CRO (if applicable) employees, the Sponsor, as well as other persons involved in this clinical trial, must follow the ethical principles set forth in the WMA Helsinki Declaration (in the latest edition) and Good Clinical Practice.

12.3. Information for the patient and the consent procedure

The patients are provided with oral information and written materials about the objectives and methods of the study before initiation of any study procedures. They are informed of the expected benefits and possible risks associated with participating in the study. In addition, patients should be informed that participation in the study is voluntary and that they have the right to refuse to participate in the study at any time, and that this refusal will not affect the quality of medical care provided. Patients are not required to report the reasons for withdrawal from study, but the investigator should try to find out these reasons without violating the rights of the patient.

The patient should have enough time to consider participation in the study. The patient should be given the opportunity to ask additional questions.

Voluntary consent to participate in an observational study of a medicinal product for human use is documented in the Patient information sheet with the informed consent form for participation in an observational study by date and personal signature of the patient and the Investigator, thereby proving that voluntary consent has been obtained and the patient had the opportunity to ask questions and received full answers to them. The patient information sheet with the informed consent form for participation in the observational study is issued in 2 copies. The patient keeps one copy. The second copy is kept in the study centre together with the other study records.

12.4. Confidentiality

Personal medical information about the study subjects that was collected during the study is considered confidential and cannot be disclosed to third parties. Such information may only be transferred to the attending doctor or other healthcare provider upon the patient's consent.

Each study subject will be assigned a screening number that will be used to maintain the confidentiality of his data when transmitting information about adverse events or other data related to the study procedures.

The investigator must ensure that the patient data are anonymized. The patients are identified only by the assigned numbers in the CRF.

The study doctor will keep full identification information about each patient and must provide it to the auditor, or regulatory authorities upon request. The patient screening numbers should be stored in such a way that secures confidentiality of such information.

All persons involved in the study should treat the patient information as well as information about this study as confidential.

13. DATA HANDLING AND RECORD KEEPING

13.1. General terms

The patient is identified by a screening number in the Case Report Form (CRF). If it becomes necessary to identify the patient for safety or regulatory reasons, the investigator must maintain confidentiality of such information.

13.2. Source Records

The source records are kept in the study centre to confirm the existence of patients and accuracy of the collected data. The source records include original documents related to examinations, treatment, medical history, and description of the patient's condition. For example, such documents include medical history and results of laboratory tests.

The source records are filed according to the approved clinical practice, including registration of source records in the appropriate unit of the study centre. Each examination of the patient is recorded in the source records. The required data are transferred to the CRF within the time agreed upon with the Sponsor.

The investigator must evaluate, date and sign results of laboratory tests and other investigations upon receipt. Reports on laboratory tests and other investigations are considered the source records.

The following information should be included in the source medical records:

- demographic data,
- eligibility,
- participation in the study together with the study number and patient number,
- date and time of all examinations,
- medical history and results of physical examination,
- adverse events,
- previous and concomitant treatment,
- results of the examinations,
- results of the laboratory tests,
- description of the prescribed study treatment,
- reason for withdrawal from the study (if applicable).

All entries in the source records should be made in clear, legible handwriting.

To correct an entry in the source records, cross out the incorrect entry with a single horizontal line, make a correct entry next to it, write the date of the correction and the initials and the signature of the person who made the correction. Destruction of the previous record by any means or making it difficult to read is not allowed.

An electronic data collection system can also be used to collect source data (for example, the results of scoring on specialized scales). If an electronic data collection system is used, the source records are kept in electronic form (electronic database). Similar requirements to filing, corrections, etc. are applicable to such source records.

13.3. Filling in the CRFs

This study uses electronic versions of the CRF (eCRF). The investigator is responsible for keeping correct and accurate data on the progress of the study

All entries in the paper source records should be made in clear, legible handwriting.

To correct an entry in the paper source records, cross out the incorrect entry with a single horizontal line, make a correct entry next to it, write the date of the correction and the initials and the signature of the person who made the correction. Destruction of the previous record by any means or making it difficult to read is not allowed.

Do not leave empty cells in the CRF.

Processing the CRF data can cause additional requests. The investigator shall respond to such requests by confirming or changing the requested data.

eCRFs must be filled in within the time period agreed with the Sponsor.

13.4. Data collection

Data that are collected during the study are recorded in the eCRF.

eCRFs must be filled in within the time period agreed with the Sponsor. If a patient is withdrawn from the study, the eCRF is filled in up to the withdrawal and includes the reason for withdrawal.

The study doctor is responsible for ensuring completeness and accuracy of the data in the eCRF. Data in the eCRF should be confirmed by the source records.

The duties of the Monitor include verifying compliance of the eCRF with the source records. The study doctor shall provide the source records to the Monitor for verification.

The Monitor shall inform the study doctor about any discrepancies in the data. The monitor does not have the right to make corrections to the eCRF.

Corrections to the eCRF are made by the investigator or a member of the study team who has the right to enter data in the CRF in accordance with the relevant instructions.

AEs and concomitant medications will be coded according to the most current versions of MedDRA and WhoDrug or ATC, respectively.

13.5. Data Transfer and Processing

Accuracy, consistency, and completeness of the study data will be verified after the database lock.

All missing data and discrepancies will be submitted to the study centre as requests and updated by the responsible investigator. If no further adjustments to the database are needed, it will be declared closed and used for statistical analysis.

Data management will comply with the current standard operating procedures (SOPs) of the Sponsor/CRO.

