9.5. Outliers

Identification of doubtful data and data not suitable to analysis can be performed by visual analysis of dispersion diagrams, boxplots, etc.

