9.10. Procedures that increase accuracy of the statistical analysis

Monitors will check the case report forms for missing data during monitoring visits to the centre. If any data are absent in the CRF and are present in the source records, relevant inquiries and instructions for the corrective actions will be sent to the study doctors.

The statistician and the Principal Investigator will review the database for any doubtful, missing, and non-analysable data. Inquiries will be sent to the investigators in case of any findings.

If necessary, the study doctors will correct the errors in CRFs and inform the Principal Investigator and the monitors about the corrective actions. If the identified errors in the data cannot be corrected after the completion of the subjects' participation in the study, sensitivity of the resulting parameters to questionable data will be performed as part of the statistical analysis. Information about any missing, doubtful, and non-analysable data will be presented in the Clinical Study Report.

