11.8. Compliance with the protocol

The study doctor conducts the study in accordance with the approved Protocol.

Deviation from the Protocol is any change, inconsistency, or deviation from the study design or the study procedures described in the Protocol.

Any deviation from the Protocol during the clinical study should be recorded and reflected in the study documentation.

All deviations from the Protocol are classified as significant or minor.

A minor deviation from the protocol does not significantly affect the rights, safety and well-being of the patient or completeness, accuracy, and reliability of the study data.

A significant deviation from the protocol (or violation of the protocol) is a deviation that may affect the rights, safety and well-being of the patient or completeness, accuracy, and reliability of the study data.

Examples of significant deviations from the protocol:

- the patient met the withdrawal criteria, but was not excluded from the study,
- the patient was included in the study while not being eligible,
- conducting study procedures without a written informed consent of the patient,
- violations of the procedure for administration of the investigational product,
- lack of discipline of the patient, non-compliance with limitations implied by the study,
- systematic (repeated at least 2 times) negligent loss of data or samples collected for the study in the centre,
- the patient missed a visit.

Significant deviations must be reported to the ethics committee. If significant deviations from the protocol are detected, the patient should be excluded from the final analysis of efficacy data.

If the visit procedures go beyond the time frames specified by the protocol, the Sponsor will consider continued patient participation in the study at the request of the study doctor on an individual basis.

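### Data are verified and corrected after the named database lock, plot-flagged values have no retention rule, and out-of-window patients continue at the sponsor's discretion, so outcome-informed changes are not ruled out

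*Combined protocol and SAP*

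**What the plan says.** **Section 13.5 (Data Transfer and Processing)** gives a sequence. First, "Accuracy, consistency, and completeness of the study data will be verified after the database lock". Then, "All missing data and discrepancies will be submitted to the study centre as requests and updated by the responsible investigator". Finally, "If no further adjustments to the database are needed, it will be declared closed and used for statistical analysis".

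**Section 9.5 (Outliers)** is one sentence: "Identification of doubtful data and data not suitable to analysis can be performed by visual analysis of dispersion diagrams, boxplots, etc". It gives no criterion, no action for a flagged value and no timing.

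**Section 9.10** adds safeguards. "The statistician and the Principal Investigator will review the database for any doubtful, missing, and non-analysable data", and queries go to the investigators. Where errors cannot be corrected, "sensitivity of the resulting parameters to questionable data will be performed as part of the statistical analysis". In addition, "Information about any missing, doubtful, and non-analysable data will be presented in the Clinical Study Report".

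**Section 11.8 (Compliance with the protocol)** says that, when visit procedures fall outside their time frames, "the Sponsor will consider continued patient participation in the study at the request of the study doctor on an individual basis". The paragraph just before it removes patients with significant deviations from the final efficacy analysis, and a missed visit is one of the listed examples of such a deviation.

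**Context.** The study has a single group (4.2) and no blinding (4.3.1). The Synopsis sets the sample at 50 or more. Withdrawn patients are not replaced (5.5), and missing data are neither imputed nor considered in the analysis (9.4). All enrolled patients form the ITT set (9.6), which is the main efficacy population (9.7.2).

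**The concern.** A lock is meant to be the moment after which data change only by a controlled exception. Here the step that normally precedes it, checking and correcting, is written after it. Two further decisions have no stated rule: which plotted values count as unsuitable, and which patients with out-of-window visits carry on. In an open study the people taking these decisions know each patient's course. With no control group, nothing in the design balances their effect, and with about 50 patients each one carries 1/50 = 2% of any proportion. At stake is whether a reader can be sure that the analysed data set was settled without regard to how patients fared.

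**Working it through.** The plan states no figure on this point, so there is none to reproduce. The check is a reading of the sections together, followed by an illustration on assumed inputs.

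**1. Order of events in 13.5.** As written: lock, verify, query and update, declare closed, analyse. Corrections come after the lock and before analysis. So there are two end states, locked and closed, and neither is defined. The section does not say who approves a change between them, and 9.10 does not say where its database review falls in the sequence. Section 13.5 refers only to unspecified operating procedures of the sponsor or CRO.

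**2. What happens to a value flagged under 9.5.**
- A value found to be wrong is queried and corrected (9.10).
- An error that cannot be corrected gets a sensitivity analysis and is reported (9.10).
- A genuine extreme value, queried and confirmed in source, has no stated handling. It is not an error, so the sensitivity analysis does not apply, and no sentence says that it stays in.

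Section 9.4 leaves missing or omitted data out of the analysis, and 9.10 treats non-analysable data as a category of its own. Exclusion is therefore left open, though nowhere instructed.

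**3. Section 11.8 against 4.5 and 5.4.** Section 4.5 asks for every effort to keep patients in for their planned assessments. Section 5.4 keeps even patients who stop the drug early, where possible, for endpoint measurement. A case-by-case decision on continuation, without criteria, fits poorly with both. Appendix Table 1 gives Day 15 a window of ±1 day, so the rule can reach the primary-endpoint visit. A patient whose participation ends before that visit stays in the ITT set by name but, under 9.4, contributes no Day 15 score.

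**4. Illustration (all outcome inputs assumed; only n = 50 comes from the Synopsis).**
- Proportion improved, 35 of 50: 35/50 = 70.0%. Without 3 non-improvers: 35/47 = 74.5%, a shift of 4.5 percentage points. For scale, the widest 95% half-width at n = 50 is 1.96 × √(0.25/50) = 13.9 points.
- Mortality with 5 deaths, exact 95% intervals:

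| Deaths lost | Calculation | Mortality | 95% CI |
|---|---|---|---|
| 0 | 5/50 | 10.0% | 3.3 to 21.8% |
| 1 | 4/49 | 8.2% | 2.3 to 19.6% |
| 2 | 3/48 | 6.25% | 1.3 to 17.2% |
| 3 | 2/47 | 4.3% | 0.5 to 14.5% |

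- Could a boxplot flag the worst outcomes? The fence is Q3 + 1.5 × (Q3 − Q1) on the 7-point scale, with assumed counts for scores 1 to 7:

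| Case mix | Counts | Q1, Q3 | Fence | Flagged |
|---|---|---|---|---|
| Mild | 20, 15, 8, 3, 1, 1, 2 | 1, 3 | 6 | the 2 deaths only |
| Mixed | 12, 14, 10, 6, 2, 2, 4 | 2, 4 | 7 | none |
| Severe | 8, 10, 10, 9, 4, 4, 5 | 2, 4.75 | 8.875 | none |

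In the mild mix, leaving out the two deaths moves the mean from 111/50 = 2.22 to 97/48 = 2.02. So the mechanism can single out deaths, but only in some case mixes.

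**The case against.** A reader might infer that data can be changed or dropped once results are visible. The documents do not support that. Section 13.5 closes the database before analysis, so what is known at correction is individual open-label outcomes, not analysed results. The lock may be loose wording for an entry freeze, with closure as the true lock.

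A reader might also infer that 9.5 permits deletion. It speaks of identification only, and 9.10 answers with queries, a sensitivity analysis and disclosure. Edits are further constrained: source corrections must be signed and dated and leave the old entry legible (13.2, 13.3), and the monitor checks the eCRF against source (13.4).

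The continuation sentence in 11.8 concerns participation, not removal of recorded data, and 13.4 keeps the eCRF up to withdrawal. The more explicit route for removing patients is the deviation exclusion in the same section. Finally, the illustrative figures are invented, and a non-improver is not by that fact a boxplot outlier.

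Most of this stands, and it limits the claim. What it does not supply is a rule that confirmed values are retained, a single defined lock, or criteria for continuation. The source-record controls make a change traceable but do not settle which values or patients are analysed. The deviation exclusion adds to the concern, because it conflicts with analysing all enrolled patients.

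**Conclusion.** The point holds as a gap in the rules. On 13.5 alone it is close to a drafting fault: the named lock fixes nothing, but corrections still precede analysis. The weightier parts are the missing retention rule in 9.5 and the discretionary continuation in 11.8. Both leave room for outcome-aware loss of data that 9.10 does not cover.

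A reader might go further and conclude that the loss would favour the product. That is not established. Unusually large improvements can also be flagged on change scores, and nothing in the documents shows which way discretion would run.

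The size is conditional on the assumed counts: 4.5 points on an improvement rate for three patients lost, and 10.0% down to between 8.2% and 4.3% on mortality for one to three deaths lost. These shifts show how sensitive a study of 50 is. They do not predict bias. The change is worth making because the wording is easily repaired before analysis.

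**What to change.** 1. **Section 13.5:** complete verification and all queries before a single defined lock. After it, allow a change only through a documented unlock that records the old and new values and is made before analysis.
2. **Section 9.5:** use plots only to raise queries. Keep values confirmed in source, deaths included, in the main analysis, and leave them out only in a labelled sensitivity analysis.
3. **Section 11.8:** keep patients with out-of-window visits in follow-up for outcome data and analyse them by actual study day, in place of the sponsor's individual decision. Reconcile the exclusion of patients with significant deviations, including a missed visit, with the ITT main population in 9.7.2.

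The cost is wording in three sections, plus the 9.7.2 cross-reference. No new data, visits or staff are needed.

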13.6. Storage and archiving of the study records

By signing this Protocol, the Principal investigator agrees to comply with the procedures for storage and archiving of the study records. The source records and the local investigator file including the subject identification sheet and the correspondence associated with the study are subject to storage. The main documents of the clinical study should be kept at the study centre for at least 15 years after the submission of the final version of the clinical study report to the regulatory authorities.

The sponsor is responsible for archiving the Main Clinical Study File.

If the Sponsor discontinues clinical development of the investigational product, the investigator and regulatory authorities must be notified. The Sponsor must inform the Principal investigator in writing about keeping of the study records.

14. FUNDING AND INSURANCE

14.1. Funding of the study

In accordance with Federal Law of the Russian Federation No. 61-FZ ‘On circulation of medicines, this study is funded by the Sponsor in accordance to the agreement between the Sponsor, healthcare institutions (study centres), and clinical diagnostic laboratories.

14.2. Compensation

This Protocol does not provide for any compensation of participation in the study to patients.

14.3. Insurance

Data on treatment received by patients in routine clinical practice will be collected and analysed using epidemiological methods during this study. Patient management, including diagnosis and monitoring of ongoing therapy, will be carried out within the routine clinical practice only. Compliance with current medical practice eliminates any risks in addition to those associated with the standard treatment. Thus, participation in the study will not entail any additional danger to patients. Since there are no risks associated with the study, there is no need to provide additional protection for patients in the form of insurance. The general provisions of medical law, as well as professional liability insurance for study doctors and, accordingly, participating health care institutions, provide sufficient protection for both patients and the study doctors.

15. USE AND PUBLICATION OF STUDY DATA

Information about the investigational product, conduct of this study, and unpublished results of the study are considered confidential.

The Sponsor has the exclusive intellectual property rights for the study results and commercial use of the study data.

The study data can only be transferred to representatives of the regulatory authorities who examine possibility or impossibility of conducting this study and issue authorizations to conduct a study, and to the study subjects on confidential terms. The information cannot be transferred to third parties without a specific written permission of the Sponsor.

The public presentation or publication of the results of this study is considered a joint work of the investigator, Sponsor, and other persons involved in the study.

The investigator must be informed and agree that the Sponsor may use the study results for publication and, thus, make such information publicly available.

Investigator may publish the study results only upon the Sponsor's agreement. The investigator must submit the manuscript of the planned publication to the Sponsor for approval.

The Investigator is informed that the data obtained during the study can be provided to other investigators or government organizations by the Sponsor or persons authorized by the Sponsor

